**Table JAIN.6.4. Imputation Techniques for Various Variables**

Efficacy and Health Outcome Endpoints for 24-week interim analyses	Imputation Method
IGA (0,1), EASI75, 4-point Itch NRS improvement	NRI a,b , pMI a , Tipping point a
EASI90, SCORAD75	NRI a,b , pMI a
EASI percent change, ADSS Item 2 change, Skin Pain NRS change	MMRM a,b , mLOCF a , pMI a , mBOCF a
All remaining categorical measures	NRI a
All remaining continuous efficacy and health outcome measures	MMRM a , mLOCF a
Efficacy and Health Outcome Endpoints for 52-week interim analyses	
IGA (0,1), EASI75, 4-point Itch NRS improvement	NRI a,b
EASI90, SCORAD75	NRI b
IGA(0,1,2), EASI <=7, SCORAD <=25, DLQI <=5	NRI a,b
All remaining categorical measures	NRI b
EASI percent change, ADSS Item 2 change, Skin Pain NRS change	MMRM b , mLOCF b
All remaining continuous efficacy and health outcome measures	MMRM b , mLOCF b
Efficacy and Health Outcome Endpoints for Period 3 and/or Period 4 analyses	
IGA (0,1), EASI75, 4-point Itch NRS improvement	mLOCF c
All remaining categorical measures	mLOCF c
EASI percent change, ADSS Item 2 change, Skin Pain NRS change	mLOCF c
All remaining continuous efficacy and health outcome measures	mLOCF c

Abbreviations: ADSS = Atopic Dermatitis Sleep Scale; EASI = Eczema Area and Severity Index score; EASI75 = 75% improvement from baseline in Eczema Area and Severity Index score; EASI90 = 90% improvement from baseline in Eczema Area and Severity Index score; IGA = Investigator's Global Assessment for AD; mBOCF = modified baseline observation carried forward; mLOCF = modified last observation carried forward; MMRM = mixed model repeated measures; NRI = nonresponder imputation, NRS = Numeric Rating Scale; pMI = placebo multiple imputation; SCORAD75 = 75% decrease from baseline in Scoring Atopic Dermatitis values.

Notes: missing data related to COVID-19 may be imputed using the method specified in Section 6.3.7.

a Analyses utilizing the primary censoring rule.

b Analyses utilizing the secondary censoring rule.

c Analyses utilizing the Long-Term Extension Substudy censoring rule, or Long-Term Extension Non-responder censoring rule.

### 6.3.1. Nonresponder Imputation

An NRI method can be justified based on the composite strategy (ICH E9R1) for handling intercurrent events. This imputation procedure assumes that the effects of treatments disappear after the occurrence of the intercurrent event. It will be the primary imputation method for the analysis of categorical efficacy and health outcomes variables such as IGA (0,1) and EASI50/75/90.

All categorical endpoints will utilize the NRI method after applying the primary censoring rule to patients who permanently discontinued study drug or were rescued (described in Section 6.2.2.2). Additionally, all primary and key secondary categorical endpoints will utilize NRI after applying the secondary censoring rule. For analyses which utilize either of the censoring methods, randomized patients without at least 1 postbaseline observation will also be defined as nonresponders for all visits. As well, patients who are missing a value prior to

discontinuation or rescue (if censoring on rescue) (that is, the patient is missing an intermediate visit) will be imputed as nonresponders at that visit only.

### **6.3.2. Mixed Model for Repeated Measures**

For the continuous secondary and exploratory efficacy and health outcome variables, such as EASI score and Scoring Atopic Dermatitis (SCORAD) score, data after the occurrence of intercurrent events (including application of any of the censoring rules) will be set to missing. Mixed model repeated measures analyses will be performed to mitigate the impact of missing data. This approach assumes that missing observations are missing-at-random (missingness is related to observed data) during the study and borrows information from patients in the same treatment arm taking into account both the missingness of data and the correlation of the repeated measurements.

Essentially, this method tries to measure the effect of initially randomized treatments had all patients remained on their randomized treatment throughout the study. For this reason, the MMRM imputation implies a different estimand (hypothetical strategy [ICH E9 R1]) than the one used for NRI on categorical outcomes. A placebo multiple imputation (pMI) or modified baseline observation carried forward (mBOCF) may be done to bridge the gap between the 2 imputation procedures.

All continuous endpoints will utilize MMRM after applying the primary censoring rule to patients who permanently discontinued study drug or who were rescued (described in Section 6.2.2.2). All key secondary continuous endpoints will also utilize MMRM after applying the secondary censoring rule.

### **6.3.3. Modified Last Observation Carried Forward**

A modified last observation analysis is performed by carrying forward the last postbaseline assessment for the continuous measures, assuming that effects of treatments remain the same after the occurrence of the intercurrent event (after application of the primary censoring rule). After mLOCF imputation, data from patients with non-missing baseline and at least 1 postbaseline observation will be included in the analyses. These mLOCF analyses help ensure that the maximum number of randomized patients who were assessed postbaseline will be included in the analyses.

For patients who experience any intercurrent event at any time, the last non-missing postbaseline observation on or prior to this event will be carried forward to subsequent time points for evaluation. If a patient does not have a non-missing observed record (or one imputed by other means) for a postbaseline visit prior to discontinuation or rescue, the last postbaseline record prior to the missed visit will be used for the visit.

For patients who entered the Period 3 and Period 4 treatment, the mLOCF in Period 3 and Period 4 will be performed by carrying forward the last available assessment if the treatment dosage did not change at the time of the last available assessment, which could be the assessment in Period 2, Period 3, or Period 4. If a patient was re-randomized at Week 52 and the treatment dosage

changed on/after Week 52, the mLOCF will be performed by carrying forward the last available assessment after the dosage change (Week 52), and before the censoring rule's cut-off date. The observed values after the censoring rule's cut-off date (i.e., retreatment such as dose up-titrated back to presubstudy dose) will not be carried forward. If Week 52's value is used as the Baseline, then the post-baseline (after Week 52) value could be carried forward to subsequent time points for evaluation.

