
To compare the efficacy of baricitinib 4-mg + TCS, baricitinib 2-mg + TCS, or baricitinib 1-mg + TCS to placebo + TCS in AD during the double-blind placebo-controlled treatment period as assessed by patient-reported outcome measures
	
 • Percent change from baseline in Itch NRS at Weeks 52, 24, 16, 4, and 1 • Proportion of patients achieving a 4-point improvement in Itch NRS at 24 weeks • Mean change from baseline in the total score of the POEM at 16 weeks • Mean change from baseline in the PGI-S-AD scores at 16 weeks • Mean change from baseline in HADS total scores at 16 weeks • Mean change from baseline in the DLQI total scores at 16 weeks • Mean change from baseline in the WPAI-AD total scores at 16 weeks • Mean change from baseline in the EQ-5D-5L total scores at 16 weeks

Substudy: Randomized Downtitration These are prespecified objectives that will be not be adjusted for multiplicity
	

All Patients Entering the Substudy To evaluate the change in clinical response after treatment downtitration from baricitinib
 
 • 4-mg to 2-mg compared with patients who are rerandomized to remain on baricitinib 4-mg • 2-mg to 1-mg compared with patients randomized to remain on baricitinib 2-mg 
Patients Entering the Substudy with IGA 0 or 1 To evaluate the change in clinical response after treatment downtitration from baricitinib
 
 • 4-mg to 2-mg compared with patients who are rerandomized to remain on baricitinib 4-mg • 2-mg to 1-mg compared with patients randomized to remain on baricitinib 2-mg 	
 • Proportion of patients with a response of IGA 0, 1, or 2 assessed at 16 weeks after rerandomization (Week 68) and Week 104 • Proportion of patients with a response of IGA 0 or 1 assessed at 16 weeks after rerandomization (Week 68) and Week 104 • Proportion of patients with a response of EASI75 from baseline assessed at 16 weeks after rerandomization (Week 68) and Week 104 • Time to retreatment (time to IGA \geq3)

Patients Not Entered into Substudy These are prespecified objectives that will not be adjusted for multiplicity
	

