5.1.3. Period 3: Double-Blind, Long-Term Extension

Patients who complete the study through Week 52 will progress into the double-blind long-term extension phase through Week 104 (Visit 22). Daily diary collection will continue through Week 68 (Visit 18) of Period 3.

Concomitant use of background TCS therapy will continue during this treatment period as described in Section 7.7.2.

5.1.3.1. Randomized Downtitration Substudy at Week 52

At Week 52, all patients will be evaluated for substudy eligibility. To be eligible, a patient must meet all of the following criteria:

- have an IGA 0, 1 (Responder) or 2 (Partial responder) at Week 52
- have not used high- or ultra-high potency TCS in the last 14 days (potency classification in [Appendix 7](#))
- do not currently have study drug interrupted
- have been assigned to baricitinib 2-mg or 4-mg at baseline (assessed by interactive web-response system [IWRS])

Treatment

Treatment in the substudy is illustrated in [Figure JAIN.1](#). Patients eligible for the substudy will be rerandomized at a 1:1 ratio at Week 52 based on the baricitinib treatment group assigned at baseline:

- 4-mg QD rerandomized to baricitinib 4-mg QD, or baricitinib 2-mg QD
- 2-mg QD rerandomized to baricitinib 2-mg QD, or baricitinib 1-mg QD

Note: Intensification of emollients and TCS may be continued or initiated to control worsening and unacceptable symptoms of AD any time during this treatment period. For management of TCS, follow the guidelines in [Section 7.7.2](#).

Retreatment

During the substudy, if worsening of AD symptoms occurs such that IGA increases to ≥ 3 , the patient will be automatically retreated with their presubstudy baricitinib dose. When the IGA is ≥ 3 , the investigator should reinstate background TCS therapy (e.g., triamcinolone 0.1% cream and/or hydrocortisone 2.5% ointment), provided the patients are not currently using TCS, and may prescribe high- or ultra-high-potency TCS following the guidelines for use of Rescue Therapies ([Section 7.7.5](#) [Rescue Therapy]). An unscheduled visit may be needed to assess worsening of symptoms and to perform clinical safety and efficacy assessments immediately before retreatment.

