The time period for safety analysis of the 24-week interim analysis will be following criteria whichever occurs first:

- up to last dose plus up to 30 days in the study
- the first dose in Period 3
- up to dose change or up to the data cutoff date

The time period for safety analysis of the 52-week interim analysis will be following criteria whichever occurs first:

- up to last dose plus up to 30 days in the study
- the study discontinuation date
- up to dose change
- the first dose date in Period 3

**The time period for safety analysis of the 104 interim analysis** will be following criteria whichever occurs first:

- up to last dose plus up to 30 days in the study
- the study discontinuation date
- up to dose change date due to rescue

- up to dose change date due to retreatment
- the first dose in Period 4
- up to the data cutoff date

**The time period for safety analysis of the final analysis** will be following criteria whichever occurs first:

- up to last dose plus 30 days or up to last date in the study
- the study discontinuation date
- up to dose change

**Long-Term Extension (LTE) Substudy Population:** The LTE Substudy Population is defined as the patients who received at least one study medication in Period 3 of Study JAIN, and entered the downtitration substudy. Additionally, those patients who did not met study discontinuation criteria in Period 3 and continued in Period 4 will be considered in the analysis set.

**Long-Term Extension(LTE) Substudy Relapse Population:** for a subset of patients in the LTE Substudy Population defined as above who experienced a relapse in Period 3 or Period 4 (IGA $\geq$ 3 after Week 52).

**Long-Term Extension(LTE) Non-responder Population:** The LTE Non-responder Population is defined as the patients who received at least one study medication in Period 3 of Study JAIN, and IGA $\geq$ 3 at Week 52. Additionally, those patients who did not met study discontinuation criteria in Period 3 and continued in Period 4 will be considered in the analysis set.

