### **6.2.2. General Considerations for Analyses for the 24-Week, 52-Week, , 104-Week Interim Analysis, and Final DBL**

**Period 2** starts at randomization (Visit 2, Week 0) and ends with the visit at Week 52 (Visit 14) or the early discontinuation visit (between Weeks 0 and 52).

**24-week interim analysis** will be done when all the patients complete Week 24 assessment (Visit 10) or discontinue study or treatment before the Week 24 assessment.

**52-week interim analysis** will be done when all the patients complete Week 52 assessment (Visit 14) or the early termination visit (between Weeks 0 and 52).

**Period 3** starts at re-randomization (Visit 14, Week 52) and ends with the visit at Week 104 (Visit 22) or the early discontinuation visit (between Weeks 52 and 104).

**104-week interim analysis** will be conducted when all the patients complete Week 104 assessment (Visit 22) or the early termination visit (between Weeks 0 and 104).

**Period 4** starts at (Visit 22, Week 104) and ends with the visit at Week 200 (Visit 28) or the early termination visit (between Weeks 104 and 200). For the final DBL, efficacy endpoints beyond week 104 will be exploratory in nature and will be analyzed in a descriptive way using observed data.

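### The extension mLOCF rule lets retained-dose patients carry forward their Week 52 entry value but denies this to down-titrated patients, so the randomised substudy arms are scored differently

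*SAP*

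**What the plan says.** SAP 6.3.3 sets the Period 3 and 4 carry-forward source by whether the dose changed:

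- **Dose unchanged.** The last available assessment is carried forward "if the treatment dosage did not change at the time of the last available assessment, which could be the assessment in Period 2" or in a later period. SAP 6.2.2 says that Period 2 "ends with the visit at Week 52 (Visit 14"), so the Week 52 rating is a Period 2 value.
- **Dose changed by re-randomisation.** Here "the mLOCF will be performed by carrying forward the last available assessment after the dosage change (Week 52") and before the censoring cut-off.
- **Exception.** Where Week 52 serves as the baseline, only later values are carried forward, whatever the dose.

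Protocol 5.1.3.1 requires substudy entrants to "have an IGA 0, 1 (Responder) or 2 (Partial responder) at Week 52", and "Patients eligible for the substudy will be rerandomized at a 1:1 ratio at Week 52 based on the baricitinib treatment group assigned at baseline". The affected endpoint in Protocol Table JAIN.2 is "Proportion of patients with a response of IGA 0, 1, or 2 assessed at 16 weeks after rerandomization (Week 68) and Week 104". The substudy population in SAP 6.2.1 is "the patients who received at least one study medication in Period 3 of Study JAIN, and entered the downtitration substudy"; it requires no assessment after Week 52. Table JAIN.6.4 lists mLOCF as the only imputation for Periods 3 and 4.

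**The concern.** Re-randomisation is what makes 4-mg/4-mg versus 4-mg/2-mg, and 2-mg/2-mg versus 2-mg/1-mg, fair comparisons. A missing-data rule that depends on the randomised dose undermines that fairness. In the retained arm, a patient with nothing usable after Week 52 is scored on the value that qualified the patient for entry, and that value satisfies the IGA 0–2 endpoint by definition. The same holds for IGA 0/1 within the subset entering with IGA 0/1. An otherwise identical patient in the down-titrated arm has no value. What is at stake is the mLOCF estimate bearing on the substudy's question: whether a lower dose keeps the response.

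**Working it through.** **The plan's own figures.** The SAP gives no sample size, power or missing-data rate for the substudy. The only design figure is power above 90% for EASI75 at Week 16. It reproduces (94.4% for 4-mg and 98.6% for 2-mg versus placebo, at 20% versus 45% and two-sided alpha 0.025) but has no bearing here.

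**Which endpoints the exception leaves exposed.** SAP 6.2.2.1 and Table JAIN.6.9 use the Week 0 baseline for EASI endpoints and no baseline for IGA, so the Week 52-baseline exception does not protect them. It does protect substudy endpoints such as change in Itch NRS or DLQI. The substudy censoring rule in SAP 6.3 is the same in both arms and does not remove the difference.

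**Size for IGA 0–2.** Let d be the share of each arm with no usable value after Week 52 by the analysed visit, and p the response rate among the rest. Both are assumed equal in the two arms, so there is no true dose effect.

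- Retained dose: (1−d)p + d
- Down-titrated: p if such patients are excluded, or (1−d)p if they count as nonresponders
- Artificial gap: d(1−p) if excluded, or d if nonresponders

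| d | p | Retained | Down, excluded | Down, nonresponder | Gap, excluded | Gap, nonresponder |
|---|---|---|---|---|---|---|
| 2% | 50% | 51.0% | 50.0% | 49.0% | 1.0 | 2.0 |
| 2% | 80% | 80.4% | 80.0% | 78.4% | 0.4 | 2.0 |
| 5% | 50% | 52.5% | 50.0% | 47.5% | 2.5 | 5.0 |
| 5% | 80% | 81.0% | 80.0% | 76.0% | 1.0 | 5.0 |

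**In whole patients (assumed counts).** Take 30 per arm, 2 per arm with no usable later value, and 18 responders among the other 28. Retained: (18 + 2)/30 = 66.7%. Down-titrated: 18/28 = 64.3% or 18/30 = 60.0%. Scoring alone produces 2.4 or 6.7 points.

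**IGA 0/1 among all entrants.** Only a share q of carried Week 52 values are IGA 0/1, so the gap is d(q−p) if excluded or dq if nonresponders. With q = 40% and p = 50%, d = 2% gives −0.2 or 0.8 points, and d = 5% gives −0.5 or 2.0. The sign can reverse. The same holds for EASI75, because a carried Week 52 value need not be a response.

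**Week 52 nonresponders.** In the 1-mg and placebo pairs every patient changes dose, so one rule applies. Only 2-mg/2-mg versus 2-mg/4-mg is split. There the carried value is IGA 3 or more, a nonresponse on the IGA endpoints. With 30 per arm, 2 unassessed and 30% response among the rest, 2-mg/2-mg scores 0.30 × 28/30 = 28.0%. 2-mg/4-mg scores 30.0% if its unassessed patients are excluded, and also 28.0% if they are nonresponders.

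**After the fix.** Both arms score (1−d)p, and the gap is zero for any common d and p.

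**The case against.** Four points count against giving this much weight.

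- **Few patients can be affected.** IGA and EASI are scheduled at Weeks 56, 60, 64 and 68. Early discontinuers are to have a termination visit, and the protocol asks for assessment before rescue. One usable later value puts both arms on the same logic. This stands, although the number need not be zero: SAP 6.3 censors results after permanent drug discontinuation, so a termination visit may be unusable.
- **The rule has a rationale.** mLOCF assumes that the treatment effect persists. A Week 52 value reflects the dose that a retained patient still takes, whereas it would credit a down-titrated patient with the former dose. That is coherent within each arm, but it does not make the two arms comparable.
- **Nothing inferential depends on it.** SAP 6.2.2.3 provides no tests in Periods 3 and 4, and Table JAIN.6.9 pairs mLOCF with observed data, which lack this asymmetry. This stands and limits the importance.
- **The artefact is small against noise.** With 30 per arm and 60% response, the standard error of a difference is √(2 × 0.6 × 0.4/30) = 12.6 points. This is true, but the artefact comes from the scoring rule and is avoidable.

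**Conclusion.** The rule as stated is wrong for a randomised comparison, and its expected impact is small. For IGA 0–2 it favours the retained dose by 0.4–2.5 points if unassessed down-titrated patients are excluded, or 2–5 points if they count as nonresponders. These figures assume d of 2–5% and p of 50–80%, equal in both arms; the documents supply neither. The effect is confined to descriptive mLOCF displays, mainly at Weeks 68 and 104.

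A reader might infer more than the documents support:

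- **That down-titration is made to look worse on every endpoint.** Automatic response holds only for IGA 0–2, and for IGA 0/1 in the subset entering with IGA 0/1. For IGA 0/1 in all entrants and for EASI75 the gap may shrink or reverse.
- **That the unassessed down-titrated patient leaves the denominator.** The SAP does not say so. Its general inclusion sentence asks for a baseline and at least one postbaseline observation. With a Week 0 baseline, Period 2 values might satisfy that.
- **That every up-titration comparison in nonresponders is biased.** Only one of the three re-randomised pairs is split, and the protocol's objective outside the substudy is the long-term effect of dose, not staying versus increasing.
- **That the artefact runs to Week 200.** SAP 6.2.2 says that efficacy beyond Week 104 uses observed data, while Table JAIN.6.9 lists both methods to Week 200, so this cannot be asserted.

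**What to change.** In SAP 6.3.3, replace the dose-dependent source with one rule for every re-randomised arm: carry forward only assessments made after the first Period 3 dose and on or before the censoring cut-off. Stating on or before also settles whether a value on the cut-off date counts; the general paragraph includes that date, while the dose-change sentence says only before it.

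Count patients with no such assessment as nonresponders for categorical endpoints, identically in all arms, and report their number per arm. If those numbers differ between arms, the reader can then see it. Rerun the Week 68 and Week 104 mLOCF summaries under this rule. Because the Week 104 database lock has passed, identify the change as made after that lock and disclose any difference.

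The cost is a sentence or two in the SAP, a program change and a rerun. No new data are needed. Retained-dose percentages may fall slightly.

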### **6.3.4. Placebo Multiple Imputation**

The pMI method will be used as an additional analysis when an intercurrent event occurs for the analysis of the primary efficacy endpoint, IGA (0,1) with  $\geq 2$ -point improvement, as well as the key secondary endpoints at Week 16 (Visit 8) and Week 52 (Visit 14), where applicable. The primary censoring rule will be applied to these sensitivity analyses.

The pMI assumes that the statistical behavior of drug- and placebo-treated patients after the occurrence of intercurrent events will be the same as if patients are treated with placebo. Thus, in the effectiveness context, pMI assumes no pharmacological benefit of the drug after the occurrence of intercurrent events but is a more reasonable approach than mLOCF because, unlike mLOCF, it accounts for uncertainty of imputation and therefore does not underestimate standard errors, and it limits bias by taking into account study/placebo effects. In the efficacy context, pMI is a specific form of a missing not at random analysis expected to yield a conservative estimate of efficacy.

Data are processed sequentially by repeatedly calling SAS® PROC MI to impute missing outcomes at visits  $t=1,.., T$ .

1. *Initialization:* Set  $t=0$  (baseline visit)
2. *Iteration:* Set  $t=t+1$ . Create a dataset combining records from drug- and placebo-treated patients with columns for covariates  $\mathbf{X}$  and outcomes at visits  $1,..,t$  with outcomes for all drug-treated patients set to missing at visit  $t$  and set to observed or imputed values at visits  $1,..,t-1$ .
3. *Imputation:* Run Bayesian regression in SAS® PROC MI on this data to impute missing values for visit  $t$  using previous outcomes for visits 1 to  $t-1$  and baseline covariates. Note that only placebo data will be used to estimate the imputation model since no outcome is available for drug-treated patients at visit  $t$ .
4. Replace imputed data for all drug-treated patients at visit  $t$  with their observed values, whenever available up to permanent study drug discontinuation and/or rescue (if censoring on rescue). If  $t < T$  then go to Step 2, otherwise proceed to Step 5.
5. Repeat steps 1-4,  $m$  times with different seed values to create  $m$  imputed complete datasets.

*Analysis:* For each completed dataset, use the model as would have been applied had the data been complete for the continuous outcome. For the primary and secondary key efficacy endpoints of IGA (0,1), EASI75, EASI90, SCORAD75, and 4-point improvement from baseline

in Itch NRS, the binary outcomes will be derived from the imputed data for each patient before fitting into the analysis model. A logistic regression model will be applied.

The number of imputed datasets will be  $m=100$  and a 6-digit seed value will be pre-specified for each analysis. Within the program, the seed will be used to generate the  $m$  seeds needed for imputation. The initial seed values are given in [Table JAIN.6.2](#).

